	
interval must be observed prior to restarting vadadustat after the last dose of rescue medication, and treatment may be resumed after the following intervals:
 
 • 2 days after last dose of epoetin rescue • 7 days after last dose of darbepoetin alfa rescue • 14 days after last dose of methoxy polyethylene glycol-epoetin beta rescue. 
Following ESA rescue, the study medication should be resumed at the same dose as previously used or one dose higher and adjusted according to the Dose Adjustment Algorithms.
 
2. RBC Transfusion: Investigators will use their local institution’s transfusion guidelines when determining whether to transfuse a study subject. In general, in the event of an acute or severe loss of blood, a RBC transfusion should be administered as clinically indicated. In less severe instances but where there may be worsening of anemia or moderate to severe symptoms of anemia, RBC transfusions are permitted at the discretion of the Investigator given the medical necessity. Reasons for RBC transfusion will be captured in the appropriate CRF. Study medication (vadadustat or darbepoetin alfa) may be continued during the transfusion period.

Phlebotomy	
If a subject’s Hb exceeds 14.0 g/dL or the rate of rise of Hb raises concern to the Investigator, the subject may be phlebotomized based on the Investigator’s judgment. The method of phlebotomy will be in accordance with the investigative site’s standard clinical practice.

Study Medication Stopping Rules	
Study medication must be permanently discontinued if a subject meets one of the criteria.
 
 • ALT or AST >3x Upper Limit of Normal (ULN) and total bilirubin >2x ULN • ALT or AST >3x ULN and INR >1.5 • ALT or AST >8x ULN • ALT or AST remains >5x ULN over 2 weeks* • ALT or AST >3x ULN with symptoms (e.g., fatigue, nausea, vomiting, right upper quadrant pain, fever, rash) or eosinophilia 
*Re-challenge generally should be avoided with ALT or AST >5x ULN unless there are no other good therapeutic options.

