7.5.5.2 Permanent Discontinuation of Study Medication

Subjects who permanently discontinue study medication prior to global study completion are expected to continue to be followed post discontinuation of study medication. These subjects are to have their EOT visit at the time of permanent discontinuation of study medication, have the Follow-up visit 4 weeks after EOT visit and continue to be followed through global study completion. At global study completion, each subject will have an End of Study (EOS) assessment to complete participation in the study. Receipt of rescue therapy is not a reason for permanent study medication discontinuation. While receiving ESA rescue, subjects must temporarily discontinue study medication but should resume study medication following the end of rescue therapy.

For subjects who permanently discontinue study medication, the Investigator will resume standard of care treatment, including ESAs and iron therapy, as deemed appropriate.

It is important to continue to follow subjects that permanently discontinue study medication.

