9.3.9 End of Treatment (EOT) Visit

The EOT visit will be performed at the time a subject permanently discontinues study medication or for subjects on study medication at the time of notification of global study completion (See [Appendix A: Schedule of Activities](#)).

At the EOT visit, the following activities/procedures will be performed:

- Vital signs including heart rate and blood pressure (assessed in seated position after 5 minutes of rest and prior to blood draws), as well as weight
- Laboratory Procedures:

- Random spot urine sample for uACR
- CBC (without differential)
- Serum chemistry including serum creatinine and eGFR
- Liver function tests
- Iron indices
- Biomarkers
- CRP
- Exploratory samples
- Safety assessments:
 - AE assessment
 - RBC transfusions and ESA rescue
 - Therapeutic phlebotomy
 - MACE endpoint questionnaire
- Recording of concomitant medications
- Drug reconciliation: Study medication (vadadustat or darbepoetin alfa) reconciliation will be conducted per the pharmacy manual instructions.
- Question subject regarding dosing compliance and whether they have experienced any problems related to the dosing of study medication (vadadustat or darbepoetin alfa)
- Visit Registration in IWR

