9.4 Study Medication Stopping Rules

Study medication must be permanently discontinued if a subject meets one of the criteria in Table 2 below

Table 2. Study Medication Stopping Rules

ALT or AST >3x ULN and total bilirubin >2x ULN	Permanently Discontinue Treatment
ALT or AST >3x ULN and INR >1.5	Permanently Discontinue Treatment
ALT or AST >8x ULN	Permanently Discontinue Treatment
ALT or AST remains >5x ULN over 2 weeks *	Permanently Discontinue Treatment

ALT or AST >3x ULN with symptoms including e.g., fatigue, nausea, vomiting, right upper quadrant pain, fever, rash or eosinophilia	Permanently Discontinue Treatment
--	-----------------------------------

* Re-challenge generally should be avoided with ALT or AST >5 times ULN unless there are no other good therapeutic options.

ALT: alanine transferase; AST: asparagine transferase; INR: international normalized ratio; ULN: upper limit of normal

See Section 10.1.1, Adverse Events for reporting requirements related to a subject being permanently discontinued based on meeting the laboratory abnormalities list above in [Table 2](#).

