If new elevations in ALT or AST >3 times ULN, **without** an elevation of total serum bilirubin >2 times ULN are identified, the following steps are to be taken:

- Temporary discontinuation of Investigational Medicinal Product (IMP);
- Repeat testing of ALT, AST, ALP, and total bilirubin, should be completed within 48 to 72 hours to confirm the abnormalities and to determine trend;
- IMP should not be resumed until monitoring indicates abnormalities have resolved or have stabilized.

Details on the management of subjects with other ALT and AST abnormalities are further described in [Section 9.4, Study Medication Stopping Rules](#).

Worsening of Anemia – In this study, it is possible that some subjects may experience a worsening of anemia. As the primary endpoint of this study assesses Hb response, worsening of anemia is captured as part of this efficacy parameter. Worsening of anemia should not be

considered an AE unless the worsening of anemia is associated with a cause *other than* the subject's CKD.

Transplantation – During this long-term study, it is anticipated that some subjects may receive a kidney transplant. These events will not be recorded as AEs. Subjects will discontinue study medication for receipt of a kidney, other solid organ, hematopoietic stem cell or bone marrow transplant and should continue with the Schedule of Activities and safety assessments as described in [Section 7.5.5.2, Permanent Discontinuation of Study Medication](#).

Malignancy – During this long-term study, some subjects may develop a newly diagnosed malignancy or a recurrence of a malignancy. At the discretion of the Investigator, these subjects may continue study medication (vadadustat or darbepoetin alfa). For reporting of adverse events of malignancy, see [Section 10.1.2 Serious Adverse Events](#).

Renal-Related Events - Some subjects will experience a progression of their CKD over the course of this study as part of the natural course of the disease. In addition, the study population is prone to experience acute, transient loss of kidney function of different etiologies, sometimes concomitantly complicated by progression of CKD.

To ensure consistent reporting of renal events, the following guidelines are to be used when reporting a renal-related AE:

- The following situations **should always be reported as SAEs** with seriousness criterion “medically important,” if no other seriousness criteria are met (see Section 10.1.2, Serious Adverse Events):

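### The liver stopping rule requires permanent discontinuation, but the footnote on one of its criteria leaves re-challenge open, so the text does not settle whether a restart is allowed

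*Protocol*

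**What the plan says.** All references are to the Amendment 7 text of the protocol.

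- **Synopsis, Study Medication Stopping Rules:** "Study medication must be permanently discontinued if a subject meets one of the criteria". Five criteria follow. The fourth, "ALT or AST remains >5x ULN over 2 weeks", is the only one with an asterisk, and its footnote reads "Re-challenge generally should be avoided with ALT or AST >5x ULN unless there are no other good therapeutic options".
- **Section 9.4:** "Study medication must be permanently discontinued if a subject meets one of the criteria in Table 2 below". Table 2 lists the same five criteria, each with permanent discontinuation as the action. The same row carries the same footnote: "Re-challenge generally should be avoided with ALT or AST >5 times ULN unless there are no other good therapeutic options".
- **Section 10.1.1:** a new ALT or AST elevation above 3x ULN without bilirubin above 2x ULN leads to a temporary stop and repeat tests within 48 to 72 hours, and "IMP should not be resumed until monitoring indicates abnormalities have resolved or have stabilized".
- **Section 7.5.5.2:** for permanent discontinuation, "These subjects are to have their EOT visit at the time of permanent discontinuation of study medication". The Follow-up visit comes 4 weeks later.
- **Section 9.3.9:** the same timing, "The EOT visit will be performed at the time a subject permanently discontinues study medication".
- **Section 8.4.10:** study medication may be given until the EOT visit.
- **Section 7.5.5.4 and Appendix A note [c]:** after discontinuation, visits and assessments are flexible. The preferred data set in 7.5.5.4 is end-of-study status, the MACE questionnaire and AE assessment.
- **Section 11.5:** subjects who stop study medication should stay on the planned visits and assessments unless they withdraw consent.

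**The concern.** A rule that makes a stop both mandatory and permanent leaves nothing to re-challenge. A footnote that discourages re-challenge except in some circumstances presupposes that a restart can happen. Both are attached to the same criterion, in both places where the rule appears, so giving one section precedence over another does not remove the conflict.

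This is a liver-safety rule in an open-label trial at approximately 390 sites. Amendment 7 added Section 9.4 in response to FDA guidance on potential drug-induced liver injury. Two investigators with identical results could act differently, each citing the same table. A monitor could not say from the text whether a restart was a deviation. A subject who was restarted would also be in a position the protocol does not describe: EOT done, dosing resumed, and no clear statement of which visits and liver tests apply.

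**Working it through.** No sample size, power or event count enters this point, so there is nothing to calculate. The check is a comparison of the texts.

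**1. Rule against footnote.** The rule has one trigger (any single criterion) and one action (permanent stop). The footnote sits on the fourth criterion and leaves re-challenge open on a condition. If the action is truly permanent, the footnote's exception has no function. If the exception has a function, the action is not permanent for that criterion. The conflict is the same in the synopsis and Section 9.4, and it covers one criterion of five.

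**2. Does another section decide it?** Resumption is described in three places: Section 7.5.5.1 (temporary interruption), Section 8.4.7.1 (after ESA rescue) and Section 10.1.1 (temporary stop for the liver signal quoted above). All three concern temporary stops. Sections 7.5.5.2, 8.4.10 and 9.3.9 treat a permanent stop as the end of dosing. No section describes dosing after EOT, so the footnote has no supporting procedure.

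**3. Which liver tests would a restarted subject have?**

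| Provision | Effect on a restarted subject |
|---|---|
| Section 9.2.2 | Liver tests listed by study week through Week 208, and at EOT; silent on restart |
| Section 9 | Treatment-period visits apply while study medication is being received, so they might apply again |
| Section 7.5.5.4, Appendix A note [c] | Visits flexible after discontinuation; no liver tests in the preferred data set of 7.5.5.4 |
| Section 11.5 | Planned visits and assessments continue after stopping |

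The second and fourth rows point towards continued testing and the third points away from it. The document does not settle the question.

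**4. Temporary rule against permanent rule.** Section 10.1.1 applies above 3x ULN when bilirubin is not above 2x ULN. Of the five criteria in Table 2, only the first includes a bilirubin condition. The other four can be met with bilirubin at or below 2x ULN: above 3x with INR above 1.5, above 8x, above 5x over 2 weeks, and above 3x with symptoms or eosinophilia. A new elevation of that kind falls under both rules as worded. Section 10.1.1 closes by referring to Section 9.4 for other ALT and AST abnormalities, but it does not say that Table 2 prevails where both apply.

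**The case against.** The strongest reply is that a general rule with an asterisked exception on one row is ordinary drafting. The exception is narrow and worded as discouragement. Its condition should rarely be met, since Section 7.5.5.2 returns a discontinued subject to standard care, including ESAs and iron. This limits how often the conflict would matter. It does not remove it, because the marked row still prescribes a permanent stop.

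It can also be said that the footnote was meant for resumption after the temporary stop in Section 10.1.1. That is possible, but it is attached to a permanent-discontinuation criterion, and nothing in either place makes the link.

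Three stronger readings might be inferred. The documents do not support them.

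- **That the exception also reaches the above-8x ULN criterion.** The footnote's threshold would include such values, but the asterisk marks only the 2-week criterion, and a footnote qualifies the row it marks.
- **That a restarted subject has no protocol-required liver tests.** Sections 9 and 11.5 can both be read as keeping the schedule in force. Sections 10.1.1, 10.3.3 and 10.3.7 add repeat testing or follow-up of the event itself. What stands is that no schedule is clearly guaranteed.
- **That re-exposure would be miscounted in the MACE analysis censored 4 weeks after discontinuation.** No section says how a restart would be coded, and the SAPs, which may say, are not at hand. That analysis supports a MACE assessment that is descriptive in this study. Under Section 11.5 the primary MACE analysis uses data on and off treatment.

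**Conclusion.** The inconsistency is real and appears twice in the current text. It should be corrected, because a mandatory liver-safety rule ought to have one reading. Its direct extent is one criterion of five. The overlap with Section 10.1.1 extends to the four criteria without a bilirubin condition. The documents give no rate of such liver events or of restarts, so the number of subjects cannot be estimated. The footnote's own condition suggests that it would be small.

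The conclusion rests on taking the footnote at its word, as leaving re-challenge conditionally open, and on there being no procedure for dosing after EOT in the protocol. It is a finding about wording and procedure. No effect on the efficacy or MACE analyses is claimed, and no position is taken on whether re-challenge should be possible.

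**What to change.** Reconcile the mandatory sentence and the re-challenge footnote, identically in the synopsis and Section 9.4, so that only one reading remains. In the same amendment, state how Section 10.1.1 relates to Table 2 when a subject meets both.

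If any resumption after a liver stop remains possible, align Sections 7.5.5.2, 7.5.5.4, 8.4.10, 9.3.9 and 11.5, so that the timing of EOT and the visits and liver tests for a restarted subject are unambiguous. The disagreement between Sections 7.5.5.4 and 11.5 on visits after discontinuation needs resolving in either case.

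The cost is a short text amendment. It is limited to the stopping rule, Section 10.1.1 and the 7.5.5.4/11.5 disagreement if no resumption is left open, and somewhat longer otherwise. Sample size and the planned analyses are unaffected. The sponsor has to make the clinical decision.

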3 LIST OF ABBREVIATIONS

AE	adverse event
ALT	alanine aminotransferase (SGPT)
ANOVA	analysis of variance
AST	aspartate aminotransferase (SGOT)
β-HCG	beta human chorionic gonadotropin
BCRP	breast cancer resistance protein
BUN	blood urea nitrogen
CBC	complete blood count
CHF	congestive heart failure
CIOMS	Council for International Organizations of Medical Sciences
CKD	chronic kidney disease
CKD-EPI	Chronic Kidney Disease Epidemiology Collaboration
CMH	Cochran-Mantel-Haenszel
CPK	creatine phosphokinase
CRF	case report form
CRO	contract research organization
CRP	C-reactive protein
CS	clinically significant
CV	cardiovascular
CVD	cardiovascular disease
DD-CKD	dialysis-dependent chronic kidney disease
DILI	Drug-Induced Liver Injury
dL	deciliter
DNA	deoxyribonucleic acid
DVT	deep venous thrombosis
EAC	Endpoint Adjudication Committee
ECG	electrocardiogram
EDC	electronic data capture
eGFR	estimated glomerular filtration rate
EOS	end of study
EOT	end of treatment
EPO	erythropoietin
ESA	erythropoiesis-stimulating agent
ESC	Executive Steering Committee
ESRD	end-stage renal disease
EU	European Union
FDA	Food and Drug Administration
g	gram
GCP	Good Clinical Practice
GFR	glomerular filtration rate
GMP	Good Manufacturing Practice
HA	health authority
Hb	hemoglobin
HDL	high-density lipoprotein

HF	heart failure
HIF	hypoxia-inducible factor
HIFPH	hypoxia-inducible factor prolyl-hydroxylase
HIF-PHI	hypoxia-inducible factor prolyl-hydroxylase inhibitor
IC ₅₀	50% inhibitory concentration
ICH	International Conference on Harmonisation
ID	identification
IDMC	Independent Data Monitoring Committee
IDMS	isotope dilution mass spectrometry
IEC	independent ethics committee
IMP	Investigational Medicinal Product
INR	international normalized ratio
IRB	institutional review board
IV	intravenous(ly)
IWR	interactive web response
JSDT	Japanese Society for Dialysis Therapy
JSN	Japanese Society of Nephrology
KDIGO	Kidney Disease: Improving Global Outcomes
kg	kilogram
LDH	lactate dehydrogenase
LDL	low-density lipoprotein
LLN	lower limit of normal
LTFU	Lost to Follow-up
MACE	major adverse cardiovascular events
MCH	mean corpuscular (cell) hemoglobin
MCHC	mean corpuscular (cell) hemoglobin concentration
MCV	mean corpuscular (cell) volume
MedDRA	Medical Dictionary for Regulatory Activities
MI	myocardial infarction
μM	micromolar
mg	milligram
mL	milliliter
mmhg	millimeters of mercury
mRNA	messenger ribonucleic acid
NDD-CKD	non-dialysis dependent chronic kidney disease
ng	nanogram
NYHA	New York Heart Association
PD	pharmacodynamics(s)
PE	pulmonary embolism
PHD	prolyl 4-hydroxylase domain
PI	package insert
PK	pharmacokinetic(s)
PP	per protocol
PT	prothrombin time
PTT	partial thromboplastin time
QA	quality assurance

QC	quality control
RBC	red blood cell
RDW	red cell distribution width
rhEPO	recombinant human erythropoietin
ROW	rest of world
SAE	serious adverse event
SAP	Statistical Analysis Plan
SC	subcutaneous(ly)
SCr	serum creatinine
SGOT	serum glutamic oxaloacetic transaminase (AST)
SGPT	serum glutamic pyruvic transaminase (ALT)
SmPC	summary of product characteristics
SV	Screening visit
TIBC	total iron binding capacity
TREAT	Trial to Reduce Cardiovascular Events with Aranesp Therapy
TSAT	transferrin saturation
uACR	urine albumin-to-creatinine ratio
ULN	upper limit of normal
US	United States
VEGF	vascular endothelial growth factor
VHP	Voluntary Harmonisation Procedures
WBC	white blood cell
WHO	World Health Organization

4 BACKGROUND INFORMATION

Chronic kidney disease (CKD), defined as the presence of kidney damage or a decreased level of kidney function, is a major public health problem worldwide. Globally, CKD is estimated to affect between 8-16% of the population (Jha et al. 2013; KDIGO 2013). At the most advanced stages of CKD, end-stage renal disease (ESRD), patients require chronic dialysis or kidney transplantation to sustain life. Chronic kidney disease is not only a cause of ESRD, but is also a significant risk factor for cardiovascular disease (CVD), infection, cancer, and mortality (Iseki and Kohagura 2007).

Renal anemia often develops during the progression of CKD and is present in almost all patients with ESRD. Anemia is defined as a decrease in circulating red blood cell (RBC) mass that is usually detected by low hemoglobin (Hb) concentration. The causes of anemia in CKD include blood loss, shortened RBC lifespan, iron deficiency, erythropoietin (EPO) deficiency, and inflammation (Nurko 2006). Although many factors contribute to anemia in CKD, it occurs primarily due to an inadequate synthesis of EPO by the kidneys, leading to a deficiency in the production of RBC progenitor cells by the bone marrow. Also contributing to anemia in CKD are impaired iron homeostasis and iron loss, which often necessitate iron supplementation (Nurko 2006). Anemia in CKD patients usually occurs when the glomerular filtration rate (GFR) falls below 60 mL/min/1.73 m², and is present in >90% of the patients undergoing dialysis (CKD Stage 5) (Goodkin et al. 2011).

The main impact of anemia on organ function is reduced oxygen delivery to tissues leading to a constellation of symptoms including fatigue, shortness of breath, and exercise intolerance (Stauffer and Fan 2014). In patients with anemia related to CKD, compensatory changes occur in cardiac structure and function, including an increase in cardiac output, the development of left ventricular hypertrophy, and, eventually, the development of heart failure (Metivier et al 2000). Risk of stroke also increases with anemia, which may be an underlying mechanism leading to stroke in CKD (Abramson et al., 2003; Iseki and Kohagura 2007). Other consequences from anemia in CKD patients include impaired cognitive function, sleep disorders, and depressed immune function, which can impact the quality of life in these patients (Iseki and Kohagura 2007; NICE 2011). Overall, anemia contributes to a poorer prognosis in patients with CKD (Nurko 2006; Iseki and Kohagura 2007).

Erythropoiesis-stimulating agents (ESAs) administered either intravenously (IV) or subcutaneously (SC), along with oral or IV iron therapy, are currently the cornerstones for treating anemia in patients with CKD. Treatment with exogenous recombinant ESAs can raise Hb levels, relieve symptoms, and reduce the complications of anemia, including RBC transfusions which carry the risks of infection, iron overload, and impact candidacy for kidney transplantation.

Clinical practice guidelines and prescribing information for approved ESAs and guidelines provided by the United States (US) Food and Drug Administration (FDA), the European Union (EU), the Japanese Society of Nephrology, and the Japanese Society for Dialysis Therapy Guideline Committee differ slightly in their recommendations for treatment of renal anemia, as summarized in Table 1.

Table 1 Treatment Guidelines and Prescribing Information for Renal Anemia in NDD-CKD

KDIGO guidelines	Treatment should occur in symptomatic patients and when Hb generally falls below 10 g/dL (Kidney Disease: Improving Global Outcomes [KDIGO] 2012).
US darbepoetin alfa label	Same as other approved ESAs, but also recommend that if Hb exceeds 10 g/dL in adults not on dialysis, the dose of ESA should be reduced or interrupted (darbepoetin alfa [Aranesp®] US Package Insert 2017).
EU practice guidelines	Recommend that in high-risk patients with non-dialysis dependent CKD (NDD-CKD), treatment with ESAs should be initiated when the Hb levels are between 9 g/dL and 10 g/dL, although in low-risk patients and those in whom a clear benefit of quality of life can be foreseen, the initiation of ESA therapy could be considered at higher Hb levels (Locatelli 2013). Detailed information on darbepoetin alfa in the EU is available on the European Medicines Agency web site.
Japan practice guidelines	JSDT recommends that ESA treatment be initiated when Hb is below 11 g/dL following a diagnosis of renal anemia in NDD-CKD. JSN 2013 does not provide a clear recommendation or maintenance range for Hb. Both guidelines recommend that if the Hb exceeds 13 g/dL, the dose of ESA should be reduced or interrupted. In patients with CVD or complications, ESA treatment should be reduced or interrupted if the Hb exceeds 12 g/dL (Tsubakihara 2010 ; Japanese Society of Nephrology 2014).

Abbreviations: CVD = cardiovascular disease; ESA = erythropoietin-stimulating agent; EU = European Union; Hb = hemoglobin; JSDT = Japanese Society for Dialysis Therapy; JSN = Japanese Society of Nephrology; KDIGO = Kidney Disease: Improving Global Outcomes; NDD-CKD = non-dialysis dependent chronic kidney disease; US = United States

The majority of patients with CKD currently receive interventional therapy in the form of iron therapy, and may initiate therapy with an ESA if other interventions fail and Hb levels fall below 9 to 11 g/dL, dependent upon local clinical practice guidelines.

A number of large, prospective, randomized controlled trials in CKD (Stages 3 to 5) have explored the potential benefit of ESAs in patients with CKD with respect to overall mortality, cardiovascular (CV) events, and progression of CKD with higher Hb targets (≥ 13 g/dL) ([Besarab et al. 1998](#); [Drüeke et al. 2006](#); [Singh et al. 2006](#); [Pfeffer et al. 2009a](#); [Pfeffer et al. 2009b](#)). These trials did not demonstrate the expected beneficial effects of correcting anemia on these outcomes, but suggested an increased risk of death and CV events when targeting higher Hb levels ([Besarab et al. 1998](#); [Drüeke 2006](#); [Singh et al. 2006](#); [Pfeffer et al. 2009a](#); [Pfeffer et al. 2009b](#)). Additional analyses from these trials suggest that the risk of death or CV events appears to be highest in CKD patients who fail to respond to ESAs, as indicated by lower achieved Hb levels and higher average ESA dose requirements ([Szczecz et al. 2008](#); [Solomon et al. 2010](#)). This suggests that in some subjects the ESAs themselves, and not the Hb level, may be causative of the increase in events. This is supported by studies in CKD patients on dialysis with naturally high Hb levels and no increase in CV events ([Goodkin et al. 2011](#)).

The risks identified with ESAs from these trials have led to changes in prescribing information and practice guidelines in the US, the EU, and Japan that guide clinicians toward more cautious use of ESAs and targeting lower Hb levels. In the US, the mortality and CV risks associated with ESAs are outlined in a black-box warning in the prescribing information of ESAs with a recommendation to use the lowest dose possible to avoid transfusions. While no similar major warnings exist in the EU Summary of Product Characteristics (SmPC) or on the approved labeling for ESAs in Japan, the EU SmPCs for ESAs do suggest caution with the use of these

drugs, with a recommendation to keep Hb levels below 12 g/dL, while the Japanese practice guidelines recommend ESA treatment be reduced or interrupted if the Hb exceeds 12 g/dL in patients with CVD or complications. Further, recent EU clinical practice guidelines ([Locatelli et al. 2013](#)) recommend that risk factors for stroke (including a past history of stroke) and the presence of active malignancy or a past history of malignancy should be taken into account when making decisions to use ESAs for the treatment of anemia.

The risks associated with ESAs, including an increased risk of death and CV events, highlight the need for additional therapies that might minimize or avoid these risks when compared to currently available recombinant protein-based ESAs. Therefore, the unmet medical need for the treatment of anemia in non-dialysis dependent CKD (NDD-CKD) patients remains high, especially from a CV safety perspective. To fulfill this unmet need, the vadadustat clinical program is focused on developing an orally active therapeutic for the treatment of anemia in patients with CKD.

